9.2.3 Overall Survival

OS is defined as the date from first dose of rucaparib to the date of death due to any cause, plus 1 day. For patients who have not died as of the time of data cut-off for analysis, data will be censored at the date the patient was last known to be alive.

OS will be summarized in a Kaplan-Meier plot; however in the case of a low censoring rate, it may be summarized with descriptive statistics.

9.3 Exploratory Efficacy Analyses

The activity of rucaparib will be evaluated in molecularly-defined HRD subgroups as described below. For all exploratory efficacy analyses, ORR, PFS, and OS (as defined in [Section 9](#)) may be used as endpoints. However, not all endpoints and analyses may be performed if the subgroups become small and limit the interpretation of the results. In addition, not all samples may be tested if it becomes clear that the analysis will have limited scientific value.

9.3.1 Correlation of Biomarkers with Response to Rucaparib

In addition to the pre-specified cutpoint of 10% genome-wide LOH defining the HRD-positive population, the clinical activity of rucaparib will be evaluated in HRD-positive and HRD-negative groups defined by cutpoints across the range of all observed percent LOH values. Tumors will be analyzed by NGS to quantify the percentage of the genome with LOH and classified as HRD-positive and HRD-negative groups according to the LOH cutpoint. Outcome benefit in both groups will be evaluated.

Tumors with a deleterious alteration in a gene involved in homologous recombination repair (HRR), such as *BRCA1* and *BRCA2*, have been associated with rucaparib activity. The clinical activity of rucaparib in patients with a deleterious monoallelic or biallelic alteration in *BRCA1*, *BRCA2*, *PALB2*, *RAD51C*, and/or *RAD51D*, as well as other genes involved in homologous recombination DNA repair, will be evaluated. The activity of rucaparib in other biomarker-defined subgroups (e.g., microsatellite instability, tumor mutational burden, PD-L1 expression, gene expression profiling) may also be assessed.

9.3.2 Evaluation of Circulating Cell-free Tumor DNA as a Molecular Marker of Response to Rucaparib

Deleterious alterations in genes of the HRR pathway will also be interrogated using ctDNA extracted from baseline plasma samples. The clinical activity of rucaparib will be evaluated in subgroups of patients with a HRR gene alteration, as well as in subgroups of patients with other alterations detected in the ctDNA assay.

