9.9 Sample Size Considerations

The overall sample size was determined by considering the number of patients needed for adequate safety and activity assessment of HRD-positive patients. Based on the estimated prevalence of 60% HRD-positive patients in this population, approximately 200 patients will be enrolled into the study. This would result in enrollment of approximately 120 HRD-positive patients. The overall sample size will enable robust estimates of response for the ITT population as well as allow for an exploration to define the optimal HRD signature that correlates with response to rucaparib. The null hypothesis for response rate based on historical data in similar patient populations is $p=0.10$. With a total sample size of 200 patients, the study has greater than 90% power to reject the null hypothesis at a 5% significance level if the true response rate for rucaparib is 20%.

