3.2 Definition of HRD Signature

The HRD signature for this study is defined as the percentage of genome with loss of heterozygosity (LOH).³ Patients whose tumors have genome-wide LOH $\geq 10\%$ will be considered HRD-positive.

A mandatory tumor specimen is required for all patients; these tissue samples will be analyzed by Foundation Medicine, Inc. (FMI) using a next-generation sequencing (NGS) assay. This assay interrogates approximately 3,500 single-nucleotide polymorphisms (SNPs) across the genome and detects alterations in 310 genes.⁴ The SNPs on this panel will be used

to quantify the percentage of the genome with LOH, a marker of HRD shown to be associated with PARP inhibitor sensitivity in patients with relapsed ovarian cancer. This study will assess if LOH is correlated with PARP inhibitor sensitivity in patients with recurrent bladder cancer.

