Appendix 2 Group Sequential Interim Monitoring Plan

Introduction

This plan describes an adaptive study design for the evaluation of rucaparib in patients with locally advanced or metastatic urothelial carcinoma. The adaptive design utilizes interim analyses that allow for early stopping for futility after DMC review of futility analysis of the ITT population, the efficacy for HRD subgroups and all safety analyses.

The trial will enroll 60-200 subjects in a single experimental arm.

Objective response rate by RECIST v1.1 as assessed by the investigator will be summarized for the ITT and HRD-positive populations as well as for the exploratory HRD groups.

Primary Analysis

Let p be the true response rate. The primary analysis compares p to a performance goal of 0.10, and is thus a hypothesis test of

$$H_0 : p \leq 0.10 \quad H_1 : p > 0.10$$

Starting with a noninformative Beta(0.1,0.9) prior on p , the posterior distribution is

$$p|\text{data} \sim \text{Beta}(0.1+Y, 0.9+N-Y)$$

where Y is the observed number of responses and N is the number of complete subjects in the trial. The trial is a success if

$$\Pr(p > 0.10 | \text{data}) > 0.95$$

This threshold maintains type I error at 5%. We consider an alternative threshold (0.935) that increases type I error slightly but obtains greater power for comparison.

Design

The trial sequentially enrolls patients and interim analyses are conducted. At the time of each interim analysis, there will be N patients with a 4-month endpoint and M patients that are incomplete. Let Y be the number of responders among the complete patients.

The model computes p_{\max} , the predictive probability of trial success if the trial is followed to the maximum (targeted) sample size and all patients are followed to completion. Let W_{\max} be the number of eventual responders among the unknown patients (incomplete and currently unenrolled). The distribution of W_{\max} is a BetaBinomial(MAXN-N, 0.1+Y, 0.9+N-Y). The predictive probability p_{\max} is the probability W_{\max} results in trial success when N=200 subjects are complete.

The model indicates trial futility at any interim analysis if $p_{\max} < \text{threshold}$, indicating that there is limited probability that the trial will reach success even at the maximum sample size.

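### The exploratory LOH cutpoint scan in SAP 9.3.1 has no stated test, grid or selection correction, and no analysis uses LOH as a continuous percentage

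*SAP*

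**What the plan says.** SAP 3.2 defines HRD-positive as genome-wide LOH of at least 10%, measured as a percentage of the genome, and adds: "This study will assess if LOH is correlated with PARP inhibitor sensitivity in patients with recurrent bladder cancer". That cutpoint defines the HRD-positive population for the primary ORR analysis (SAP 3.1 and 9.1).

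SAP 9.3.1, under Exploratory Efficacy Analyses, keeps the 10% cutpoint. In addition, it evaluates activity in HRD-positive and HRD-negative groups "defined by cutpoints across the range of all observed percent LOH values" and looks at outcome in both groups. SAP 9.3 lists ORR, PFS and OS as possible endpoints and allows analyses to be dropped where subgroups are too small. SAP 10.3 makes no adjustment for multiple comparisons.

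Protocol 9.9 says the sample size will also "allow for an exploration to define the optimal HRD signature that correlates with response to rucaparib". Protocol 9.5.3.1 lists genome-wide LOH among several markers whose association with response will be explored, with patients classified by presence or absence of each marker.

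Neither document gives a test, significance level, cutpoint grid, minimum group size or selection rule for the scan. Neither gives a model with continuous LOH, or any validation of a chosen cutpoint.

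**The concern.** Whether LOH tracks response in bladder cancer is a question this study is meant to inform, since SAP 3.2 takes its evidence for the marker from ovarian cancer. One fixed split at 10% answers only part of it. The rest is left to a series of splits along the observed range.

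Looking at many splits and taking the best-looking one produces an apparent cutpoint even when LOH and response are unrelated. The best split's ORR in the LOH-high group, and its gap from the LOH-low group, are biased upward because the split was chosen for being large. This does not depend on whether a p-value is printed, and the exploratory label does not remove it. The protocol's mention of an optimal signature makes it plausible that someone will pick a cutpoint from this display, and the plan says nothing about how the optimism would then be handled.

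**Working it through.** **1. Inputs from the documents.** N = 200, null response rate 0.10 and alternative 0.20 (Protocol 9.9); Beta(0.1, 0.9) prior and posterior threshold 0.95 (SAP Appendix 2); about 60% HRD-positive, or 120 of 200 (SAP 2.3).

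**2. The plan's own figure.** No error rate is stated for the scan, so the nearest check is the primary ITT test. The smallest Y with Pr(p > 0.10 | Beta(0.1+Y, 0.9+200−Y)) > 0.95 is Y = 28. The binomial tail Pr(Y ≥ 28 | N = 200) is 0.0434 at p = 0.10, 0.683 at p = 0.15 and 0.989 at p = 0.20. These match the Fixed row of the appendix table (0.043, 0.683, 0.989) and the claim of more than 90% power in Protocol 9.9.

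**3. Assumptions for the scan, none set by the documents.** Response is independent of LOH; true ORR is 10-20%; LOH has no ties; all 200 patients have an LOH result; there is one endpoint; each cut is tested at nominal 0.05.

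Let R be the total number of responders. For a cut that puts k patients in the LOH-high group with c responders:

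- gap: d = c/k − (R−c)/(N−k)
- one-sided Fisher p: Pr(X ≥ c), with X hypergeometric (N, R, k)
- two-sided chi-square: |z| > 1.96, with z = d / √[(R/N)(1−R/N)(1/k + 1/(N−k))]

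A trial counts as a false positive if any cut on the grid crosses its limit.

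**4. Simulated results, no association, ORR 10-20%.**

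| Grid | Test | P(at least one nominally significant cut) |
|---|---|---|
| Single fixed cut, 60% positive | chi-square, two-sided | 4.4-5.3% |
| 3 quartile cuts | Fisher, one-sided | 7-9% |
| 9 decile cuts | Fisher, one-sided | 12-15% |
| 9 decile cuts | chi-square, two-sided | 23-25% |
| Every cut, at least 40 per side | Fisher, one-sided | 18-20% |
| Every cut, at least 20 per side | Fisher, one-sided | 22-26% |
| Every cut, at least 20 per side | Fisher, two-sided | about 35% |
| Every cut, at least 20 per side | chi-square, two-sided | 41-44% |
| Every cut, full range | Fisher, two-sided | 40-47% |
| Every cut, full range | chi-square, two-sided | 60-66% |

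Nine independent tests would give 1 − 0.95⁹ = 37%. Neighbouring cuts share most of their patients, so the decile rate is lower. Scanning PFS and OS as well would raise all the multi-cut rates.

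**5. Size of the spurious gap.** At the best cut by one-sided Fisher p, with at least 20 per side, the median gap is about 7 points at ORR 10%, 8 at 15% and 9 at 20%. The 90th percentile is 13-17 points. For scale, the trial is powered for 20% − 10% = 10 points.

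**6. The alternatives.** One rank test of continuous LOH against response has a false-positive rate of 4.7-5.2%. To hold 5% overall with a maximally selected chi-square, the nominal p at the best cut must be about 0.008 for nine decile cuts, or about 0.003 for every cut with at least 20 per side.

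**The case against.** The strongest reply is that SAP 9.3.1 plans no inference here. It names no p-value, level or selection rule, and its text fits a plain display of ORR by cutpoint. The work is labelled exploratory, SAP 10.3 is open about the lack of adjustment, and the 10% cutpoint is retained. That single fixed cut has no selection inflation. Protocol 9.9 calls the optimal signature an exploration, and Protocol 9.5.3.1 shows that several markers are candidates, not only an LOH threshold. SAP 2.3 restates the sample-size rationale without that phrase.

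Most of this stands, and it rules out several stronger readings:

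- A reader might infer that the plan carries a false-positive rate of about a quarter. It does not. That figure needs a particular test and grid, and other reasonable choices give anything from about 8% to over 40%.
- A reader might infer that the scan is the only LOH analysis, or that it contaminates the primary result. The prespecified cutpoint appears in the same sentence, and the primary ORR analyses do not depend on the scan.
- A reader might infer that a chosen cutpoint will be carried into a later trial. Neither document says so.

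The objection does not dispose of the gap itself. A purely descriptive display would need to be declared as one, and even then the best-looking split shows an inflated gap. Nor does it supply an analysis that uses LOH on its measured scale to address the correlation question in SAP 3.2.

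**Conclusion.** The point holds as a cheap improvement to an exploratory analysis, not as an error in the primary one. The plan evaluates LOH at cutpoints across its whole observed range without a stated test, grid or selection correction, and it never uses LOH as a continuous variable.

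The harm is conditional: it arises if the scan is read at nominal 5% or used to pick a cutpoint. In that case, with no association and 200 evaluable patients, the false-positive chance runs from about 8% (three quartile cuts, one-sided Fisher), through 22-26% (every cut with at least 20 per side, one-sided Fisher), to above 40% (every such cut, two-sided chi-square). The median spurious ORR gap at the best cut with at least 20 per side is about 7-9 points. All of these rest on the assumptions in step 3 of the working; the spread across tests and grids is itself a reason to fix the method in advance.

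**What to change.** In SAP 9.3.1:

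- Make the main exploratory LOH analysis one logistic regression of confirmed response on continuous percent LOH, with a spline plot to show the shape.
- State that the display of activity by cutpoint is descriptive.
- For any cutpoint chosen from the data, report a permutation p-value for the maximally selected statistic and bootstrap optimism-corrected ORRs for the two groups. State the cutpoint grid and minimum group size used.

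The prespecified 10% cutpoint and the primary analyses stay as they are. The cost is a few sentences of SAP text and a little programming. The downside is that a data-chosen cutpoint will look less impressive after correction.

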9.3.3 Assessment of Molecular Changes Over Time in Plasma and Tumor Samples

Deleterious alterations in genes of the HRR pathway, and other biomarkers (eg, microsatellite instability, tumor mutational burden, gene expression profiling), will be interrogated in tumor tissue samples (when available) and ctDNA extracted from serially collected samples. Changes in the profiles observed in these samples will be evaluated for biomarkers of response to rucaparib.

9.3.4 Evaluation of Biomarkers Associated with Resistance to Rucaparib

Tumor tissue (when available) and plasma collected at the time of disease progression will be profiled to identify potential alterations associated with resistance to rucaparib. Samples may be tested using genomic, transcriptional, and proteomic assays. Analysis of ctDNA from serially collected blood samples may be performed to identify and characterize the emergence of mechanisms of resistance. The analysis will include, but not be limited to, reversions of HRR gene alterations that restore wild-type function and alterations in other components of DNA repair and oncogenic signaling pathways.

9.4 Exploratory Pharmacokinetic Analyses

In all patients with at least one PK sample collected, the trough plasma rucaparib PK data (C_{\min}) and summary statistics of C_{\min} (N, mean, StD, minimum, median, maximum, coefficient of variation [CV] %), and the mean (\pm StD) concentration versus time plot will be reported. The PK data and selected safety and efficacy endpoints will be included in exploratory population PK and exposure-response analyses, and the results will be reported separately.

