1.3.2.2.1 OVERVIEW OF CLINICAL PHARMACOLOGY

Assessment of rucaparib PK in cancer patients showed an approximate dose-proportional exposure after once daily (QD) or twice daily (BID) dosing, rapid absorption with maximum plasma concentration (C_{max}) achieved within 1.5 to 6 hours. The oral bioavailability was 36% and terminal half-life ($T_{1/2}$) was approximately 24 hours. Rucaparib was moderately bound to human plasma proteins *in vitro* (70%).

At a dose of 600 mg BID rucaparib, steady-state was achieved after approximately 1 week with approximately 4-fold accumulation. At the target clinical dose of 600 mg, a high-fat meal increased the C_{max} and area under the plasma concentration-time curve from 0 to 24 hours (AUC_{0-24h}) of rucaparib by 20% and 38%, respectively, and delayed the median time to occurrence of C_{max} (T_{max}) by approximately 2.5 hours as compared with these parameters under fasted conditions. The effect of food on rucaparib PK is not considered to be clinically significant, thus rucaparib can be taken with or without food.

In vitro, rucaparib showed slow enzymatic turnover in human liver microsomes and hepatocytes. Recombinant CYP2D6, and to a lesser extent CYP1A2 and CYP3A4, were able to metabolize rucaparib. In cancer patients, M324, a carboxylic acid, was a major inactive metabolite of rucaparib.

Drug interactions with rucaparib as a substrate were assessed in a population PK analysis. CYP2D6 phenotypes (poor metabolizers, intermediate metabolizers, normal metabolizers, and ultra-rapid metabolizers) and CYP1A2 phenotypes (normal metabolizers and

hyperinducers) did not significantly impact the steady-state exposure of rucaparib at 600 mg BID. Current smokers had overlapping rucaparib exposures as compared to nonsmokers and former smokers. Collectively, the results suggest that CYP1A2 and CYP2D6 play a limited role in rucaparib metabolism in vivo. Although in vitro rucaparib metabolism mediated by CYP3A4 was slow, a significant contribution of CYP3A4 in vivo cannot be excluded. No rucaparib dose adjustment is recommended when concomitantly administered with CYP inhibitors or inducers.

Concomitant treatment with proton pump inhibitors (PPIs) showed no clinically significant effect on rucaparib PK. No dose modification of rucaparib is required for patients who are receiving concomitant treatment with a PPI.

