5.3 Method of Assigning Patients to Treatment Groups

All patients enrolled in the study will receive rucaparib at an initial dose of 600 mg BID.

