u	=	Archival FFPE tumor tissue must be submitted if available. Refer to the Pathology Charter for detailed sample handling instructions.
v	=	Refer to the Laboratory Manual for detailed sample processing instructions. Cycle 1 ctDNA must be collected even if within 3 days of screening ctDNA.
w	=	To be performed at the time of tumor evaluation for Cycle 3 and in subsequent cycles coinciding with tumor scans through the 28-day Follow-up Visit.
x	=	Cycle 1 Day 1 only
y	=	A single sample should be collected as close as possible to 12 hours after the last dose has been taken and prior to the next dose. Refer to the Laboratory Manual for sample processing instructions.
z	=	Cycles 2, 3, and 4 only.
aa	=	All patients discontinued from treatment, regardless of reason, should be followed for survival and subsequent therapies every 12 weeks until death, loss to follow-up, withdrawal of consent from study, or study closure, whichever happens first. Follow-up can be performed via the telephone.

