- Concomitant medications and any surgical/medical procedures
- Hematology
- Serum chemistry (fasting is not required)
- Urinalysis

- AE monitoring
- Patients return all unused tablets and containers (empty, partially used, and/or unopened) to the study site for accountability

Patients will ingest rucaparib twice daily at about the same times every day as close as possible to 12 hours apart. Rucaparib should be taken with water and with or without food. Patients will keep all unused tablets and containers (empty, partially used, and/or unopened) and return with them to the study site for accountability at the next visit. In the event of toxicities, re-treatment or dose modification will be according to the criteria described in [Section 5.4.1](#).

7.4.3 Cycle 2 Day 1

Patients will be instructed to refrain from taking their first dose of rucaparib at home on the day of their visit to collect plasma samples for PK and the ctDNA blood sample.

Plasma samples for PK analysis should be collected before the morning dose as close as possible to 12 hours after the previous dose. If the start of the next dose is delayed, the PK sample should still be collected during this visit instead of the delayed start of the next study visit.

The following procedures will be completed before rucaparib is administered:

- Physical examination
- Weight
- ECOG performance status ([Appendix 2](#))
- Vital signs
- Concomitant medications and any surgical/medical procedures
- Hematology
- Serum chemistry (fasting is not required)
- Serum pregnancy test for women of childbearing potential
- Urinalysis
- Collect ctDNA blood sample
- Collect plasma sample for PK analyses
- AE monitoring
- Patients return all unused tablets and containers (empty, partially used, and/or unopened) to the study site for accountability
- Dispensation of rucaparib

Patients will ingest rucaparib twice daily at about the same times every day as close as possible to 12 hours apart. Rucaparib should be taken with water and with or without food. Patients will keep all unused tablets and containers (empty, partially used, and/or unopened) and return with them to the study site for accountability at the next visit. In the event of toxicities, re-treatment or dose modification will be according to the criteria described in [Section 5.4.1](#).

7.4.4 Cycle 2 Day 15

The following procedures will be completed before rucaparib is administered:

- Physical examination
- Weight
- Vital signs

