9.6 Pharmacokinetic Analyses

In all patients with at least 1 PK sample collected, the trough plasma rucaparib PK data (C_{min}) and summary statistics (N, mean, StD, minimum, median, maximum, coefficient of variation [CV]%) will be reported.

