2.2 Study Objectives and Endpoints

Table 1. Primary, Secondary, and Exploratory Objectives and Endpoints

Primary Objectives	Primary Endpoints
To evaluate objective response rate (ORR) in molecularly-defined homologous recombination deficiency (HRD)-positive and intent-to-treat (ITT) populations using a prospectively defined molecular signature.	ORR per Response Evaluation Criteria in Solid Tumor (RECIST) Version 1.1 (v1.1), as assessed by investigator, in HRD-positive and ITT populations
Secondary Objectives	Secondary Endpoints
To evaluate duration of response (DOR)	DOR per RECIST v1.1, as assessed by investigator
To estimate progression-free survival (PFS)	Disease progression according to RECIST v1.1, as assessed by the investigator, or death due to any cause
To estimate overall survival (OS)	OS
To evaluate safety and tolerability of rucaparib	Incidence of adverse events (AEs), clinical laboratory abnormalities, changes in ECGs and vital signs, and dose modifications
To evaluate steady-state pharmacokinetics (PK) of rucaparib	Trough (C_{min}) level rucaparib concentrations
Exploratory Objectives	Exploratory Endpoints
To assess biomarkers that correlate with response to rucaparib	Clinical efficacy of rucaparib in biomarker defined cohorts
To evaluate circulating cell-free tumor DNA (ctDNA) as a molecular marker of response to rucaparib	Association of cancer-related mutations detected in baseline ctDNA samples with response to rucaparib
To assess molecular changes over time in plasma and tumor samples	Association of changes in cancer-related mutations detected in plasma and tissue samples over time with response to rucaparib
To evaluate biomarkers associated with resistance to rucaparib	Biomarkers associated with resistance to rucaparib

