10 STATISTICAL / ANALYTICAL ISSUES

10.1 Handling of Dropouts or Missing Data

All data will be used to their maximum possible extent, but without any imputations for missing data. All time-to-event analyses will include censoring and the rules for deriving the censored values are described in more detail under each of the time-to-event endpoint descriptions.

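### Trough rucaparib (Cmin) is summarised with no condition on dose at sampling, recent hold or time since last dose, although the secondary objective is steady-state PK

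*SAP*

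**What the plan says.** Table 1 of the SAP lists as a secondary objective "To evaluate steady-state pharmacokinetics (PK) of rucaparib", with trough (Cmin) concentrations as the endpoint. No dose is named in either. Table 2 of the protocol says the same.

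The analysis rule in SAP section 9.4 reads "In all patients with at least one PK sample collected, the trough plasma rucaparib PK data", followed by a list of summary statistics that includes the CV, a plot of mean concentration over time, and exploratory population PK and exposure-response work to be reported separately. Protocol section 9.6 matches it: "In all patients with at least 1 PK sample collected, the trough plasma rucaparib PK data". SAP section 10.1 adds "All data will be used to their maximum possible extent, but without any imputations for missing data". No section restricts the PK set further.

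On dosing, protocol section 5.3 states "All patients enrolled in the study will receive rucaparib at an initial dose of 600 mg BID". Section 5.4.1 then allows holds for toxicity and steps to 500, 400 and 300 mg BID. Section 6.2 adds holds around palliative radiotherapy.

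On sampling, the Table 5 footnote reads "Cycles 2, 3, and 4 only". Protocol sections 7.4.3 and 7.4.5 ask for a pre-dose draw about 12 hours after the previous dose, and then say "If the start of the next dose is delayed, the PK sample should still be collected during this visit". Section 7.6.8 says that, if the next dose is postponed or suspended, the draw should be about 12 hours after the previous dose.

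On pharmacology, protocol section 1.3.2.2.1 gives approximately dose-proportional exposure, a terminal half-life of about 24 hours, and "At a dose of 600 mg BID rucaparib, steady-state was achieved after approximately 1 week", with about 4-fold accumulation.

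**The concern.** The objective says steady state; the analysis set does not put that word into effect. A patient who has taken 400 mg BID unchanged for two weeks, a patient who stepped down two days earlier and a patient four days into a hold all satisfy the only stated condition. The first is at steady state for a lower dose. The other two are not at steady state for any dose.

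A mean over such samples belongs to no particular regimen. It could be read as the trough at the starting dose in urothelial cancer, and dose reductions for toxicity could then be mistaken for low exposure in this population. The planned plot over time has a related weakness. If reductions accumulate from Cycle 2 to Cycle 4, visit means fall because of dosing, which could be misread as a change in pharmacokinetics.

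**Working it through.** The documents give no Cmin value, CV or expected share of reduced or held patients, so there is no planned figure to reproduce. The check below covers the PK inputs and then the possible size of the effect.

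**1. Are the PK inputs coherent?** For one compartment, a 24-hour half-life and 12-hourly dosing:
- Accumulation = 1/(1 − 2^(−12/24)) = 3.41, against about 4-fold in the protocol (4.0 needs a half-life of about 28.9 hours).
- Fraction of steady state at 7 days = 1 − 2^(−7) = 99.2%, in line with about 1 week.

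The inputs agree well enough for rounded values.

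**2. What does one atypical sample contribute, relative to the 600 mg BID trough?**
- 500, 400 and 300 mg BID: 0.833, 0.667 and 0.500.
- In a hold, d days past the usual trough time: 2^(−d), which is 0.50 at 1 day, 0.125 at 3 days and 0.008 at 7 days.

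**3. Reductions unrelated to exposure.** Let f be the factor from step 2 and cv the true between-patient CV. Then mean ratio = E[f] and pooled CV = √((1 + cv²)·E[f²]/E[f]² − 1). The dose mixes are assumed.

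| Share at 600/500/400/300 | E[f] | E[f²] | CV if true CV is 50% |
|---|---|---|---|
| 90/5/3/2% | 0.972 | 0.953 | 51% |
| 70/15/10/5% | 0.917 | 0.861 | 53% |
| 50/20/20/10% | 0.850 | 0.753 | 55% |

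For the last row, E[f] = 0.50 + 0.20 × 0.833 + 0.20 × 0.667 + 0.10 × 0.500 = 0.850. The mean is thus about 3% to 15% below the 600 mg BID trough.

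Now add holds to the 30% row, taking the held samples from the 600 mg share:
- 5% of samples at 3 days: 0.65 + 0.217 + 0.05 × 0.125 = 0.873, CV 58%.
- 10% of samples at 7 days: 0.60 + 0.217 + 0.10 × 0.008 = 0.817, CV 65%.

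Over true CVs of 30% to 75%, the CV rises by about 1 to 7 points from reductions alone, and by up to about 19 points with holds (30% becomes 49%).

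**4. Reductions that track exposure.** Take lognormal exposure with true CV 50%, so s = √ln(1.25) = 0.472. Reduction is decided by a normal score with correlation ρ to log exposure, and 30% are reduced in the mix above (cut-points 0.524, 1.036 and 1.645). The mean is Σ f × P(band), with cut-points lowered by ρs.
- ρ = 0.5: band probabilities 0.613, 0.175, 0.132, 0.080; mean = 0.613 + 0.833 × 0.175 + 0.667 × 0.132 + 0.5 × 0.080 = 0.89.
- ρ = 0.8: band probabilities 0.558, 0.187, 0.153, 0.103; mean 0.87.

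A simulation of 1,000,000 patients gave the same means, with pooled CVs of 45% and 38%, both below the true 50%. With 5% of samples also 3 days into a hold, the CVs were 50% and 43%.

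The mean among patients still on 600 mg is the first band divided by 0.70: 0.613/0.70 = 0.88 for ρ = 0.5 and 0.558/0.70 = 0.80 for ρ = 0.8. Both are slightly or clearly below the pooled means of 0.89 and 0.87.

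**The case against.** The best defence is that the documents never say that visits or doses are merged. Section 9.4 says who contributes and which statistics are shown, and its plot over time points to some display by visit. That is fair as far as visits go. On dose at sampling, holds and time since dose, both documents are silent, and the only stated rule admits every sample.

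Second, the sampling instructions aim at a 12-hour trough. The Table 5 footnote and section 7.6.8 both do, and a sample drawn that way when only the Day 1 dose is delayed is a valid trough. This limits samples taken in a hold but does not remove them. If a hold began days before the visit, drawing at the visit and drawing about 12 hours after the last dose cannot both be done.

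Third, a summary of troughs as treated is a legitimate target, Cmin carries no hypothesis test, and population PK may use the dose history. This keeps the consequence modest. However, the target is not stated, and the population PK work is exploratory, is reported separately, and has no described handling of dose.

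A reader might infer that the result is bound to understate the 600 mg BID trough and to have an inflated CV. The documents do not support that. They give no rate of reductions or holds, they do not define the endpoint as the 600 mg BID trough, and step 4 shows that the CV can fall when reductions concentrate in patients with high exposure.

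**Conclusion.** The point stands as a gap between objective and analysis. A secondary objective of steady-state PK is served by a summary that has no steady-state condition and no link to dose. If any sampled patients are reduced or on hold, a pooled mean below the 600 mg BID trough is the expected direction. The size is about 3% to 15% for 10% to 50% of samples at reduced doses, and about 18% with 30% reduced plus 10% of samples seven days into a hold. These figures rest on assumed shares, approximate dose proportionality and a 24-hour half-life. No claim is made about the direction of the CV. The change is worth making because it is cheap; no primary or efficacy conclusion depends on it.

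**What to change.** In SAP section 9.4 and protocol section 9.6:

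- State the target of the Cmin summary.
- Present Cmin by visit and by dose at sampling, or dose-normalised.
- Base the steady-state summary on samples with no hold or dose change in the previous 7 days (the protocol's own time to steady state) and a draw inside a pre-specified window around 12 hours after the last dose. List all other samples with the reason.
- Label any 600 mg-only summary as a selected subset and show it beside the by-dose or dose-normalised results, since it can lie below the pooled mean when reductions follow exposure.

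Three checks go with this. Confirm that last-dose and draw times are captured: protocol section 5.4.1.4 requires dose modifications to be recorded in the eCRF, but the documents do not show that these times are. Reconcile the delayed-dose sampling instructions in protocol sections 7.4.3 and 7.4.5 with section 7.6.8. Reconcile the exploratory label in the heading of SAP section 9.4 with the secondary objective in Table 1.

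The cost is SAP and protocol wording, one by-dose table and one listing. The downside is fewer samples in the steady-state summary, with small groups at the lower doses.
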